5.5.3.1. Sensitivity Analyses

For each of the two binary key secondary endpoints, sensitivity analyses will include MI under MAR, which uses all participants with available key secondary endpoint status through Day 29. The imputation model (using PROC MI) will be informed by the observed outcomes for participants through Day 29 including treatment and prognostic factors. Participants with missing information on each key secondary endpoint through Day 29 will be imputed using monotone logistic regression. Further variables will be considered for inclusion in the MI model on the basis that they may inform missingness or be correlated with the endpoint. The final analysis model applied to the complete data set will be the same as that for the primary analysis. Treatment effect estimates from the individual completed data sets will be combined using Rubin's rules via PROC MIANALYZE.

An additional sensitivity analysis will repeat the key secondary efficacy analyses in the PPS analysis set.

5.5.4. Additional Secondary Endpoints and Analyses

Analyses of other secondary endpoints in the mFAS-non-Omicron analysis set will be conducted to support the findings of the primary and key secondary efficacy endpoints. The results of these analyses will be considered descriptive in nature and will be analyzed without any procedures to account for multiple comparisons, except as specifically noted. Analysis approaches for the other secondary endpoints (ie, non-key) are summarized in [Table 4](#). In addition to these analyses, listings of viral load based on nasopharyngeal samples; viral load, viral clearance status, viral load AUC, and time to viral clearance based on saliva samples; and medically attended visits will be provided.

Table 4: Additional Secondary Endpoint Analyses

Endpoint	Statistical Analysis Methods
COVID-19-related medically attended visits and all-cause death through Day 29	The methods for the primary efficacy endpoint will be used except without applying multiplicity adjustments (see Section 5.5.1).
Time to sustained recovery in COVID-19 symptoms through Day 29	The methods for the analysis of time to sustained resolution of COVID-19 symptoms through Day 29 will be used (see Section 5.5.3)
All-cause death through Day 29, Day 60, and Day 90	KM methodology will be used to analyze all-cause deaths. The probability of all-cause deaths by each of these time points will be estimated, along with 95% CIs for differences in the probabilities. Survival curves between ADG20 and placebo will be compared using a log-rank test. A Cox Proportional Hazard model will be used to estimate the hazard ratio. The model includes age (continuous), sex (categorical), baseline serostatus (categorical: positive, negative), baseline BMI (continuous), and baseline viral load (continuous as \log_{10} copies/mL) as covariates. Comparison of the survival distributions will use the score test for the hazard ratio from this Cox model.

Endpoint	Statistical Analysis Methods
Change from baseline in SARS-CoV-2 viral load (\log_{10} copies/mL) to Day 7 (± 1) assessed by RT-qPCR from NP samples	
Observed NP baseline and post-baseline values are used to calculate change from baseline. ANCOVA with treatment group and the prognostic factors (with observed NP baseline) as in the primary efficacy endpoint analysis as covariates. The LS mean for the point estimate in each group and 95% CIs will be presented. The difference in LS means between the ADG20 group and the placebo group and 95% CIs for the differences will be determined. The analysis will be performed on the mFAS-non-Omicron-NP with available data at Day 7. In addition, two-sample t-test will be used to compare change from baseline viral load between treatment without covariate adjustment (unadjusted mean difference).
 
If Day 7 value is missing, the earliest measurement closest to the Day 7 visit within 1 day (including scheduled and unscheduled visit) will be used.

Viral load >5 (\log_{10} copies/mL) on Day 7 (± 1) based on NP samples	The methods for the primary efficacy endpoint will be used. Analysis will be performed on the mFAS-non-Omicron-NP with available data at Day 7. Analysis will be repeated using a second definition of high viral load (viral load $>4 \log_{10}$ copies/mL).
Duration of SARS-CoV-2 viral shedding from Day 1 through Day 29 assessed by RT-qPCR from saliva samples	KM methodology will be used to analyze duration of viral shedding from Day 1 through Day 29 of SARS-CoV-2 RNA. KM curves, the number and percentage of censored observations and the median, 25 th and 75 th percentiles will be provided. Survival distributions will be compared between ADG20 and placebo using a log rank test stratified by age (categorical) and baseline serostatus. A stratified Cox Proportional Hazard model will be used to estimate the hazard ratio where the model includes age (categorical as 12-17 years, 18-65 years and >65 years) as a stratification variable and sex (categorical), baseline serostatus (categorical as positive; negative), baseline BMI (continuous) and baseline viral load (continuous as \log_{10} copies/mL) as covariates. Comparison of the survival distributions will use the score test for the hazard ratio from this Cox model. Analyses will be performed on the mFAS-non-Omicron-S.
Change from baseline in SARS-CoV-2 viral load (\log_{10} copies/mL) to Days 3, 5, 7, 11, 14, 21, and 29 assessed by RT-qPCR from saliva samples	Observed saliva baseline and post-baseline values are used to calculate change from baseline. Mixed model for repeated measures with treatment group and the prognostic factors (with observed saliva baseline) in the primary efficacy endpoint analysis as covariates. The LS mean for the point estimate in each group and 95% CIs will be presented. The difference in LS means between the ADG20 group and the placebo group and the 95% CIs for the differences will be determined. A plot of the LS means with 95% CIs by Day assessed by treatment group will be presented. The analysis will be performed on the mFAS-Non-Omicron-S with available data at each timepoint. In addition, a two-sample t-test will be used to compare change from baseline viral load between treatment at each time point without covariate adjustment (unadjusted mean difference).
SARS-CoV-2 viral clearance (Days 3, 5, 7, 11, 14, 21, and 29) assessed by RT-qPCR from saliva samples (and BLQ/not detected or not detected for NP sample for Day 7)	
In the mFAS-non-Omicron-S, the cumulative proportion of participants with viral clearance will be presented for each post-baseline time point. In the mFAS-non-Omicron-NP, the proportion of participants with viral load BLQ/not detected or not detected at Day 7 will be presented. The ADG20 arm will be compared to placebo using the analysis procedure outlined for the primary efficacy outcome.
 
In addition, these analyses will be presented for the subgroups of participants with observed baseline NP viral load >5 and $\leq 5 \log_{10}$ copies/mL.

Endpoint	Statistical Analysis Methods
SARS-CoV-2 viral load AUC (\log_{10} copies/mL) assessed by RT-qPCR from saliva samples through Day 29	An ANCOVA will be used to compare ADG20 and placebo where the prognostic factors in the primary efficacy endpoint analysis will be used as covariates. Participants in the mFAS-non-Omicron-S will be included in this analysis. The AUC from Day 1 through Day 29 will be calculated according to the linear trapezoidal rule using the measured SARS-CoV-2 viral load above the lower limit of quantification. No AUC values will be calculated when Day 1 and/or Day 29 values are missing, or if there are more than 3 values missing in the profile. In addition, two-sample t-test will be used to compare viral load AUC between treatment without covariate adjustment (unadjusted mean difference).

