Participant Population: Mild or moderate COVID-19 in adults and adolescents can typically be managed in the outpatient/ambulatory setting. Data from other SARS-CoV-2 mAb programs suggest that populations at high risk for progression of COVID-19 are likely to benefit from treatment with a mAb (see Section 1.4.1). In order to ensure similar risk of COVID-19 disease progression across the two treatment groups, enrollment will be stratified based on age. Data from several regions have consistently shown that age is the most critical factor for risk of severe COVID-19 including hospitalization, ICU stay, and death ([Docherty 2020](#); [Grasselli 2020](#); [Ko 2020](#); [Wu 2020](#); [Kim 2021](#)). Of the risk factors identified, age appears to have the most profound impact on outcomes, with significant increase in risk clearly evident around age 65 and a greater magnitude in risk than that associated with any individual co-morbidity ([Kim 2021](#)). In a cohort of more than 1.3 million patients diagnosed with COVID-19, of patients with no reported underlying health conditions, 9.6%, 15.5%, and 27.9% of patients 50-59, 60-69, and 70-79 years of age required hospitalization, respectively ([Stokes 2020](#)).

Symptom Onset Within 5 Days: Symptoms of COVID-19 generally appear from 2 to 14 days following exposure to SARS-CoV-2. A subset of individuals with initially mild or moderate symptoms may experience disease progression. For example, in a study of 138 hospitalized patients with COVID-19 pneumonia, dyspnea, and hospitalization developed after a median of 5 and 8 days, respectively, from symptom onset ([Wang 2020](#)). These data suggest a window for intervention of <7 days from onset of symptoms with a potently neutralizing antiviral mAb like ADG20 to prevent disease progression. Consistent with this hypothesis, experience with other highly potent mAbs (casirivimab/imdevimab, bamlanivimab/etesevimab, sotrovimab,

regdanvimab, and bebtelovimab) suggests that administration early in the course of infection (eg, within 5 to 7 days or less of onset of symptoms) is associated with faster resolution of symptoms and a reduction in the need for medically attended visits, including emergency room visits and hospitalizations ([Celltrion Healthcare Hungary 2021](#); [Eli Lilly and Company 2022a](#); [Eli Lilly and Company 2022b](#); [GlaxoSmithKline 2022](#); [Regeneron 2022](#)).

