4.4. Multiplicity Adjustments

To control the overall type I error rate at .05 (2-sided), a hierarchical testing procedure will be used, such that testing for the key secondary analyses difference will proceed only if the treatment difference is statistically significant in the primary analysis.

Analyses of the other secondary and exploratory endpoints will be conducted to support the findings of the primary and key secondary efficacy analyses without accounting for multiple comparisons. Nominal p-values and 95% CIs will be computed for these secondary and exploratory efficacy analyses when applicable.

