
Time to sustained resolution in COVID-19 symptoms through Day 29 will be analyzed by KM methodology and stratified Cox Proportional Hazard model. Survival curves between ADG20 and placebo will be compared using a log-rank test stratified by age (categorical as 12-17, 18-65, and >65 years). A stratified Cox Proportional Hazard model will be used to estimate the hazard ratio where the model includes age (categorical as 12-17, 18-65, and >65 years) as stratification variable and sex (categorical), baseline serostatus (categorical), baseline BMI (continuous), and

baseline viral load (continuous as \log_{10} copies/mL) as covariates. Comparison of the survival distributions will use the score test for the hazard ratio from the Cox model.

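### The log-rank test for all-cause death is the only one in the SAP not stratified by age; it is mildly conservative, and the row does not say whether it or the Cox score test leads

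*SAP*

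**What the plan says.** The all-cause death row of SAP Table 4 (section 5.5.4) reads "Survival curves between ADG20 and placebo will be compared using a log-rank test" and names no strata. The matching row of protocol Table 7-2 (section 7.8) has the same test.

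The row then adds a Cox model: "The model includes age (continuous), sex (categorical), baseline serostatus (categorical: positive, negative), baseline BMI (continuous"), with baseline viral load as the fifth covariate. It closes with "Comparison of the survival distributions will use the score test for the hazard ratio from this Cox model". So one comparison is given two tests, and neither is named as the main one.

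For symptom resolution (SAP 5.5.3) the curves are "compared using a log-rank test stratified by age (categorical as 12-17, 18-65, and >65 years"). Sustained improvement (5.5.6.2) and recovery (5.5.6.3) follow the same wording. The SAP row for viral shedding stratifies by age and baseline serostatus.

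Randomization is stratified by age (12-17, 18-65, >65) and country (SAP 4.3). That section explains why country stays out of the models. It gives no reason for leaving age out of the death log-rank. Protocol 1.3.2 says "Of the risk factors identified, age appears to have the most profound impact on outcomes".

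On status, SAP 5.5.4 says of the other secondary endpoints: "The results of these analyses will be considered descriptive in nature". SAP 4.4 adds: "Nominal p-values and 95% CIs will be computed for these secondary and exploratory efficacy analyses when applicable".

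**The concern.** When allocation is balanced within age bands, chance imbalance in age between the arms is largely removed by design. An unstratified log-rank test still carries that between-age variation in its variance. The variance is then too large, the test rejects too rarely under the null, and some power is lost. The effect grows with the strength of age as a predictor, and death is the outcome for which age is expected to matter most. Yet death is the one time-to-event endpoint whose log-rank test drops the stratum.

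At stake is the p-value likely to stand beside the Kaplan-Meier mortality curves. It would not match the design or the rest of the plan, and there is no rule for reading it if the Cox score test disagrees.

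**Working it through.** **Inputs.** From the documents: about 320 participants in the primary efficacy population (SAP 4.2), 1:1 allocation, the age strata, and the five Cox covariates. The documents give no death rate, age mix or age effect on death. Assumed ranges: 10-30% aged over 65; hazard ratio for death over 65 versus younger of 3, 5 or 10; 90-day placebo death risk of 3%, 6% or 12%; treatment hazard ratio 0.3, borrowed from the 70% relative reduction assumed for the primary endpoint.

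**1. The plan's own figures.** None is given for the death test. For the primary endpoint, with pooled variance, n per arm = [1.96√(2p̄(1−p̄)) + 1.282√(p₀(1−p₀)+p₁(1−p₁))]² / (p₀−p₁)². With 5% versus 0.05 × 0.3 = 1.5% this gives 538 per arm, 1076 in total, against 1084 stated. With 160 per arm and 12% versus 0.12 × 0.3 = 3.6%, power is 80.3%, against about 80% stated. These agree, so 160 per arm is a fair basis.

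**2. Why the unstratified test is conservative.** Let stratum k hold a share wₖ with death risk pₖ, and let p̄ be the overall risk. The true variance is roughly this fraction of what the unstratified test assumes:

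R = 1 − Σwₖ(pₖ−p̄)² / [p̄(1−p̄)], and null rejection ≈ 2[1−Φ(1.96/√R)].

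- Mild case (30% over 65, age HR 3, p̄ = 3%): risks 1.9% and 5.6%; R = 1 − 0.00028/0.0291 = 0.990; rejection 4.9%.
- Extreme case (10% over 65, age HR 10, p̄ = 12%): risks 7.4% and 53.6%; R = 1 − 0.01919/0.1056 = 0.818; 1.96/√R = 2.167; rejection 3.0%.

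**3. Simulation of the two log-rank tests.** N = 320, balanced within age band, 90-day follow-up, 4000 runs per setting (Monte Carlo standard error about 0.3 points at 5%). Selected rows, unstratified → stratified:

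| Over 65 | Age HR | Placebo death risk | Null rejection | Power at HR 0.3 |
|---|---|---|---|---|
| 30% | 3 | 3% | 4.7 → 4.8% | 25.9 → 26.1% |
| 30% | 5 | 6% | 5.0 → 5.5% | 49.0 → 49.9% |
| 10% | 5 | 6% | 4.7 → 5.0% | 47.5 → 48.9% |
| 10% | 10 | 6% | 3.5 → 5.0% | 46.2 → 49.9% |
| 10% | 10 | 12% | 3.0 → 5.0% | 77.0 → 81.9% |

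Over the whole grid, null rejection is 3.0-5.4% unstratified and 4.6-5.7% stratified. The power gain is 0.1 to 1.4 points at age HR 3-5 with 3-6% death risk, 1.2 to 3.7 points at age HR 10 with the same risks, and at most 4.9 points. That maximum needs a placebo death risk of 12%, which is the SAP's placebo rate for hospitalization and death combined.

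**4. The Cox score test in the same row.** With age generated as continuous (HR 1.5-2.5 per decade), stratifying the log-rank gains 0.0 to 3.2 points over the unstratified test. A Cox score test adjusted for age alone gains 0.4 to 5.9 points and is at least as good as the stratified log-rank in all nine settings. The data were generated with a log-linear age effect, which favours that model. With all five covariates (25% over 65, 1500 runs), power for unstratified / stratified / Cox score was 24.7-25.0 / 25.6-27.0 / 26.9-27.3% at 3% placebo mortality, 38.1-41.0 / 40.9-41.9 / 43.0-43.7% at 5%, and 68.3-71.8 / 71.7-72.8 / 73.4-75.0% at 10%.

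**5. Convergence of the five-covariate model.** With 15% seropositive (assumed), the covariate fit failed in 59-62% of runs at about 4 deaths, 41-42% at about 6, 22% at about 10 and 4-5% at about 20. Most of this arises when no seropositive participant dies, so that coefficient has no finite estimate. If deaths are unrelated to serostatus, the chance is 0.85⁴ = 52%, 0.85⁶ = 38%, 0.85¹⁰ = 20% and 0.85²⁰ = 4%.

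**6. Scale.** By Schoenfeld, power = Φ(|ln 0.3|·√d/2 − 1.96): 22% with 4 deaths, 40% with 8, 55% with 12 and 77% with 20. The number of deaths matters far more than the stratification.

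**The case against.** The case for leaving the row alone is strong on consequence. The mortality comparison is already adjusted for age, on a finer scale than three bands, by the Cox score test in the same row, and that test does about as well as the stratified log-rank or better. The endpoint is outside the hierarchy, results are descriptive, and a slightly conservative nominal p-value is still valid. The row is also coherent in itself: an unstratified log-rank beside an unstratified Cox model, where the other rows pair stratified with stratified. Protocol and SAP agree, which suggests a choice rather than a slip. All of this limits the size of the point.

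It does not explain the omission. The symptom and shedding analyses also carry an adjusted Cox score test, and their log-rank tests are stratified by age all the same. Nor would an age-stratified log-rank conflict with a Cox model that adjusts for continuous age, since both condition on age.

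A reader might go further and infer that the mortality analysis ignores age, or that the whole comparison is underpowered and below nominal type I error. The row's Cox score test contradicts that. A reader might also infer that five covariates on few deaths make the Cox test invalid and leave the log-rank as the only dependable comparison. The documents do not say so, and the simulations do not show it: null rejection of the five-covariate score test was 4.5-5.6% in one set of runs and 3.5-7.2% in another, somewhat above nominal in places. Its clear weakness is failure to converge when deaths are few.

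**Conclusion.** The point holds as a minor one, confined to the log-rank test. That test is unstratified although age is a randomization stratum and a leading predictor of death, and it departs from every other log-rank test in the SAP without a stated reason. Its null rejection is about 3 to 5%, and it gives up about 0 to 5 points of power, usually under 2 at low death rates. These sizes rest on assumed death rates, age mix, age effects and a treatment hazard ratio of 0.3.

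The type I error control described in SAP 4.4 ("To control the overall type I error rate at .05 (2-sided), a hierarchical testing procedure will be used") covers the primary and key secondary endpoints, and all-cause death is not among them. No confirmatory conclusion changes. The practical gain is a simple test that matches the design and is available when deaths are too few for the Cox model to fit, together with a clear statement of which p-value leads.

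**What to change.** In the all-cause death row of SAP Table 4 and protocol Table 7-2:

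- Stratify the log-rank test by age (12-17, 18-65, >65 years), as for the other time-to-event endpoints.
- State which of the log-rank test and the Cox score test is the main result.
- State that the stratified log-rank test stands if the five-covariate Cox model does not converge.

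The cost is a few words, with no new data. An age band with no deaths contributes nothing to the stratified statistic, so little is lost there. SAP 3.2 requires the SAP to be signed before unblinding, so the change belongs in that version. If only the SAP is edited, SAP section 1 lets it prevail over the protocol, but section 7, which records no changes from the protocol analyses, should then list this one.

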1. INTRODUCTION

This SAP describes the planned analyses for ADG20-TRMT-001 (STAMP) based on the clinical study protocol, version 6.0, dated 02-Mar-2022. In addition to the information presented in the statistical analysis section of the protocol (Section 7), which provides the principal features of analyses for the study, this SAP provides statistical analysis details/data derivations. It also documents modifications or additions to the analysis plan that are not principal in nature and result from information that was not available at the time of protocol finalization.

The STAMP study is a randomized, double-blind, placebo-controlled, multi-center adaptive study of the safety, efficacy, PK, and antiviral activity of the mAb ADG20 in the treatment of ambulatory participants with mild or moderate COVID-19 with a high risk of disease progression based on age or co-morbid medical conditions. The study will be conducted in 2 phases with data review conducted by an iDMC throughout.

PPD Biostatistics and programming team, designee of Adagio Therapeutics, Inc., will perform the statistical analysis; SAS Version 9.4 or higher will be used. If the methods in this SAP differ from the methods described in the protocol, the SAP will prevail. Any additional analysis outside of the planned analysis following the Day 29 database soft lock or the final database lock that are not performed by PPD are not included in the SAP.

The STAMP study was impacted by the emergence and global spread of the SARS-CoV-2 B.1.1.529 (Omicron) variant, which was first detected in South Africa and Botswana in November 2021. In vitro assessments of the neutralization activity of ADG20 demonstrated markedly reduced activity against authentic Omicron virus compared with prior variants such that ADG20 is unlikely to demonstrate adequate efficacy against SARS-CoV-2 infections caused by the Omicron variant. As a result, enrollment the study was suspended on 11-Jan-2022 as Omicron had become or was likely to become the predominant variant in regions enrolling the trial.

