3.4.2. Virologic Efficacy Assessments

Blood will be collected on Day 1 to test for SARS-CoV-2 antibodies. Two NP swabs will be collected on Day 1 for SARS-CoV-2 RT-qPCR, SARS-CoV-2 sequencing, and a respiratory panel assessment. One NP swab will be collected on Day 7 for SARS-CoV-2 RT-qPCR and SARS-CoV-2 sequencing. Saliva samples for SARS-CoV-2 RT-qPCR will be collected at the site on Days 1, 7, and 29, and by participants at home on Days 3, 5, 11, 14, and 21.

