4.2. Sample Size

The primary analysis is the comparison of the ADG20 arm versus the placebo arm with respect to proportion of participants infected with a non-Omicron variant of SARS-CoV-2 with a COVID-19-related hospitalization or all-cause death through Day 29.

The original required sample size was calculated based on the following assumptions obtained from a review of data from studies of other mAbs in participants with a high risk for disease progression leading to hospitalization or death prior to widespread emergence of both the Delta and Omicron variants ([AstraZeneca 2022](#); [Eli Lilly and Company 2022](#); [GlaxoSmithKline 2021](#); [Regeneron 2022](#)). The original sample size of 1084 participants was planned with 90% power, 2-sided alpha .05, and a 1:1 randomization ratio to detect a statistically significant risk reduction with a true efficacy of relative risk reduction 70% and a 5% event rate in the placebo arm.

At the time of enrollment suspension in January 2022, a total of 399 participants were randomized. Of them, approximately 320 participants will be included in the primary efficacy population of participants with a non-Omicron variant of SARS-CoV-2. Based on blinded monitoring of the primary endpoint outcomes, an aggregate event rate of approximately 9% was observed, indicating a higher placebo event rate than previously assumed and providing approximately 80% power to test the primary endpoint in the primary efficacy population given an estimated placebo event rate of 12% and the same efficacy assumption.

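### Saliva shedding times are tied by design and the SAP names no tie method for the Cox model, so the shedding hazard ratio and score test depend on an unstated choice

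*SAP*

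**What the plan says.** SAP Section 3.5.2 measures shedding from the first dose date to the first date on which virus is undetected in saliva, provided this is sustained through Day 29. Section 3.4.2 fixes when saliva is taken: at the site on Days 1, 7 and 29, and "by participants at home on Days 3, 5, 11, 14, and 21". That leaves seven post-baseline occasions. The schedule (SAP Appendix M, Protocol Table 12-1) allows ±1 day for Days 3, 5 and 7, ±2 days for Days 11, 14 and 21, and +5 days for Day 29.

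For the comparison of arms, Table 4 gives a stratified log-rank test and a Cox model stratified by age, and then says "Comparison of the survival distributions will use the score test for the hazard ratio from this Cox model". Section 5.5.3 uses the same construction for time to sustained resolution, the third key secondary: "Comparison of the survival distributions will use the score test for the hazard ratio from the Cox model". Sections 5.5.6.2 and 5.5.6.3 repeat it for sustained improvement and sustained recovery. The symptom times come from a daily diary analysed on the actual day (Appendix B).

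On software, SAP Section 1 says "SAS Version 9.4 or higher will be used". No passage in the SAP or in Protocol Sections 7.7 and 7.8 names Breslow, Efron, exact or discrete handling of ties.

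**The concern.** Cox partial likelihood assumes that no two events coincide. When several do, the analyst must choose an approximation, and with coarse times the choice changes the answer. At an event time with n at risk, d events and a fraction p of the risk set on ADG20, the Breslow score variance is d·p·(1−p). The correct conditional variance is d·p·(1−p)·(n−d)/(n−1). Breslow omits the last factor, so it overstates the information, shrinks z and moves the hazard ratio toward 1.

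At stake is the size of a listed secondary virologic estimate, which the SAP also plans to show in a forest plot (Section 5.5.6), and the p-value beside it. The SAP fixes smaller details, such as the imputation seed in Section 5.5.1.1. This choice is left to whoever writes the program.

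**Working it through.** **The plan's own figures.** No hazard ratio, event count or power is stated for any Cox endpoint. The stated figures concern the binary primary endpoint: "The original sample size of 1084 participants was planned with 90% power, 2-sided alpha .05, and a 1:1 randomization ratio", with "true efficacy of relative risk reduction 70% and a 5% event rate in the placebo arm". Pooled two-proportion formula, mean rate 0.0325:

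n per arm = [1.96·√(2·0.0325·0.9675) + 1.2816·√(0.05·0.95 + 0.015·0.985)]² / 0.035² = 0.658/0.001225 ≈ 538, so 1076 in total, close to 1084.

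For the current population ("approximately 320 participants will be included in the primary efficacy population"), 160 per arm at 12% against 3.6% gives 80.3% power, matching the SAP's approximate 80%. This confirms the scale of the data but does not bear on ties.

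**Inputs from the documents.** Two-sided alpha 0.05; 1:1 allocation; about 320 participants for the symptom endpoints; the seven saliva days and their windows; a daily diary to Day 29.

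**Assumptions.** 280 participants in the saliva set (no size is given); exponential event times; control medians of 8, 12 and 18 days; true hazard ratio 1.0, 1.4 or 1.5; two age strata; treatment the only model term. The spread grid puts about half of the visits on target and the rest uniformly over their windows.

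**Simulation.** 1000 trials per row, true hazard ratio 1.4. Tied share is Σ(d²/n)/Σd.

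| Grid, N | Control median (days) | Tied share | HR Breslow | HR Efron | Power Breslow | Power Efron | Power log-rank |
|---|---|---|---|---|---|---|---|
| Saliva on target days, 280 | 8 | 29.3% | 1.332 | 1.402 | 65.1% | 76.7% | 76.8% |
| | 12 | 23.6% | 1.344 | 1.400 | 62.7% | 72.6% | 71.9% |
| | 18 | 18.2% | 1.352 | 1.394 | 55.2% | 63.7% | 63.3% |
| Saliva spread over windows, 280 | 8 | 15.0% | 1.360 | 1.391 | 70.2% | 75.3% | 74.9% |
| | 12 | 11.5% | 1.372 | 1.395 | 68.2% | 71.6% | 71.8% |
| | 18 | 8.6% | 1.389 | 1.407 | 63.1% | 66.2% | 66.1% |
| Daily diary, 320 | 8 | 10.6% | 1.378 | 1.399 | 78.9% | 81.9% | 81.8% |
| | 12 | 7.3% | 1.383 | 1.398 | 75.8% | 77.7% | 78.1% |
| | 18 | 5.2% | 1.387 | 1.396 | 68.5% | 69.2% | 69.3% |

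Breslow costs 8.5 to 11.6 points on target days, 3.1 to 5.1 when dates are spread, and 0.7 to 3.0 on the daily diary. At a true hazard ratio of 1.5 the target-day estimate is 1.41 to 1.45 under Breslow against 1.50 under Efron. The daily-diary estimate is then 1.47 to 1.49 against 1.50, with a loss of 0.4 to 1.3 points.

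Runs with 60% to 90% of the placebo arm cleared by Day 29, and with none, half or all of the dates spread, widen the shedding ranges to those in the verdict.

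**Closed-form check.** If p is roughly constant, z under Breslow is about √(1 − tied share) times the correct z. Target days, median 12: √(1 − 0.236) = 0.874, so the effective critical value is 1.96/0.874 = 2.24. Efron power of 72.6% corresponds to a mean z of 1.96 + 0.60 = 2.56. Breslow power is then Φ(2.56 − 2.24) = Φ(0.32), about 62.5%; the simulation gave 62.7%.

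**Under the null.** On the target-day grid at hazard ratio 1.0, Breslow rejects in 3.1% to 3.4% of trials and Efron in 5.2% to 5.8%.

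**The case against.** The strongest reply is that the plan already contains a comparison free of this problem. A stratified log-rank test with the usual hypergeometric variance is specified for shedding and for the symptom endpoints, and in the table it stays within one point of Efron. This stands as regards testing. It does not repair the hazard ratio, which comes only from the Cox model, and the SAP does not say whether the log-rank or the score test governs.

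Second, the effect is conditional. SAS is named but no procedure option, so a reader who infers that the plan commits to Breslow goes beyond the text. If the programmers choose Efron or exact handling, nothing is lost.

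Third, shedding is outside multiplicity control, and Section 5.5.4 calls these results descriptive. Saliva clearance by visit, change in viral load and viral load AUC are analysed by methods in which ties play no part. This is correct, and it limits the weight of the point.

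Fourth, a reader might infer that the third key secondary, the only one of these endpoints under type I error control, is seriously harmed. The documents do not support that. Its times lie on a daily grid, and the hazard ratio is off by only 0.01 to 0.03.

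Finally, the error is conservative, so no false efficacy claim can arise from it.

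**Conclusion.** The point holds for the shedding hazard ratio and its score test, conditional on Breslow being used. With an assumed saliva set of about 280, a true hazard ratio of 1.4 and 60% to 90% of the placebo arm cleared by Day 29:

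- All samples on target days: hazard ratio about 1.32 to 1.37 under Breslow against 1.39 to 1.41 under Efron; power about 6 to 13 points lower.
- Some or all dates spread over the visit windows: power about 1 to 6 points lower. Event times are actual dates, so some spread is likely and the target-day figures are an upper case.
- Daily-diary symptom endpoints, including the third key secondary: power 0.4 to 3 points lower.

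Type I error is not inflated, and the stratified log-rank tests are untouched. The simulations omit the sex, serostatus, BMI and viral load terms of the planned models, and the event rates and effect sizes are not in the documents. This is a worthwhile clarification that changes a reported estimate, not a threat to the trial's main conclusions.

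**What to change.** State in SAP Section 5.5.3, Table 4 (Section 5.5.4), Section 5.5.6.2 and Section 5.5.6.3 that all Cox models and their score tests use the Efron (or exact) method for ties. A grouped-time complementary log-log model for shedding is an option but is not needed.

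The cost is one sentence and one procedure option, with no new data. The SAP is to be signed before unblinding (Section 3.2), and the sentence belongs in it by then.
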